1. Neurological Function Scales:

- **NIHSS:** Assesses the severity of neurological deficits (range: 0-42; higher scores indicate more severe deficits). Administered at baseline, Day 7, Day 14, and Day 90.
- **mRS:** Assesses functional independence (range: 0-6; scores 0-2 indicate good functional outcome). Administered at baseline, Day 7, Day 14, and Day 90.
- **Modified Barthel Index (MBI):** Assesses activities of daily living (range: 0-100; higher scores indicate better independence). Administered at baseline, Day 14, and Day 90.
- **EQ-5D-5L:** Assesses health-related quality of life (including mobility, self-care, usual activities, pain/discomfort, anxiety/depression; scored as a utility value ranging from -0.291 to 1.0). Administered at baseline, Day 14, and Day 90.

2. Cerebral Perfusion Parameters (CTP):

- Measured at baseline, Day 14, and Day 90: cerebral blood volume (CBV), cerebral blood flow (CBF), mean transit time (MTT), time to peak (TTP) in the infarct core and penumbra.
- Changes in perfusion parameters from baseline are used to evaluate the improvement of cerebral blood flow.

3. Infarct Volume Measurement:

- Infarct volume is measured on DWI using the ABC/2 method (A: maximum length, B: maximum width perpendicular to A, C: number of slices × slice thickness).
- Changes in infarct volume from baseline to Day 14 are used to evaluate infarct progression or regression.

5. Outcome Evaluation Indicators

(1) Primary Safety Endpoints

- **Dose-Limiting Toxicity (DLT):** Assessed within 14 days of the first dose, defined as any of the following:
 1. Grade 3-4 AE related to the study drug (CTCAE V5.0), such as severe nasal bleeding, anaphylactic reaction, or hepatic injury;
 2. Increase in NIHSS score ≥ 4 points from baseline (indicating significant neurological deterioration);
 3. Symptomatic intracranial hemorrhage (confirmed by CT/MRI and associated with neurological deterioration).

(2) Secondary Safety Endpoints

1. **SAE Incidence:** Proportion of subjects with drug-related SAEs within 90 days of the first dose;
2. **All-Cause Mortality:** Proportion of subjects who die from any cause within 90 days of the first dose;
3. **Laboratory Abnormality Rate:** Proportion of subjects with Grade ≥ 3 laboratory abnormalities (e.g., thrombocytopenia, elevated liver enzymes) within 90 days.

(3) Efficacy Endpoints

1. **Functional Outcome:** Proportion of subjects with mRS score 0-2 at Day 90;

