2. **Neurological Improvement:** Mean change in NIHSS score from baseline to Day 14 and Day 90; proportion of subjects with NIHSS score reduction ≥ 4 points at Day 14;
3. **Functional Independence:** Mean change in MBI score from baseline to Day 90; proportion of subjects with MBI score ≥ 60 (indicating moderate independence) at Day 90;
4. **Quality of Life:** Mean change in EQ-5D-5L utility value from baseline to Day 90.

(4) Exploratory Endpoints

1. **Infarct Volume Change:** Mean change in infarct volume from baseline to Day 14;
2. **Cerebral Perfusion Improvement:** Mean changes in CBF, CBV, MTT, and TTP from baseline to Day 14;
3. **Correlation Analysis:** Correlation between baseline characteristics (e.g., age, NIHSS score) and efficacy outcomes.

6. Study Protocol Flow and Evaluation Indicators

First Visit [Baseline (Day 0)]

1. **Informed Consent:** The investigator explains the study protocol to the subject/legal representative, who signs the informed consent form if willing to participate.
2. **Screening Assessments:**
 - Demographic and clinical data collection;
 - Vital signs measurement;
 - Laboratory tests: CBC, clinical chemistry, coagulation function, serum electrolytes, infectious disease screening, tumor markers, urinalysis, pregnancy test (if applicable);
 - Imaging examinations: NCCT, DWI, MRA/CTA, chest X-ray, 12-lead ECG;
 - Neurological scales: NIHSS, mRS, MBI, EQ-5D-5L.
3. **Eligibility Confirmation:** The investigator reviews the inclusion/exclusion criteria and confirms eligibility.
4. **Study Drug Administration:**
 - Nasal mucosa pretreatment with hyaluronidase (150 U per nostril);
 - Instill the first dose of hUC-MSC-sEV-001;
 - Measure vital signs 30 minutes after administration.
5. **Documentation:** Record combined medications, rehabilitation therapy plans, and any AEs.

Second Visit (Day 7 ± 1)

1. **Safety Assessments:**
 - Vital signs measurement;
 - Laboratory tests: CBC, clinical chemistry, urinalysis;
 - AE monitoring and recording.
2. **Efficacy Assessments:**
 - Neurological scales: NIHSS, mRS.
3. **Documentation:** Record combined medications and rehabilitation therapy progress.

Third Visit (Day 14 ± 2)

1. Safety Assessments:

- Vital signs measurement;
- Laboratory tests: CBC, clinical chemistry, coagulation function, serum electrolytes, infectious disease screening, tumor markers, urinalysis;
- Imaging examinations: 12-lead ECG, DWI, FLAIR, CTA/CTP;
- AE monitoring and recording (including SAE follow-up).

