- **Source Documents:** Medical records, laboratory reports, imaging films, and informed consent forms are stored in the hospital's medical record department or study office for 30 years after study completion.
- **Electronic Data:** The EDC database and backup files are stored on a secure server with restricted access. The data are retained for 30 years after study completion.
- **Statistical Analysis Data:** The locked database and statistical analysis code are stored in a secure location and retained for 30 years after study completion.

11. Statistical Analysis

(1) Statistical Analysis Sets

- **Full Analysis Set (FAS):** Includes all randomized subjects who receive at least one dose of the study drug. Missing efficacy data are imputed using the last observation carried forward (LOCF) method.
- **Per Protocol Set (PPS):** Includes subjects in the FAS who comply with the study protocol (e.g., complete all visits, receive all 4 doses of study drug, no major protocol violations). This set is used for sensitivity analysis of efficacy outcomes.
- **Safety Analysis Set (SAS):** Includes all subjects who receive at least one dose of the study drug. This set is used for safety analyses (adverse events, laboratory abnormalities).

(2) Descriptive Statistics

- **Continuous Variables:** Presented as mean \pm standard deviation (SD) for normally distributed data, or

median (P25, P75) for non-normally distributed data. Examples include age, NIHSS score, and infarct volume.

- **Categorical Variables:** Presented as frequency (percentage). Examples include gender, hypertension status, and mRS score categories (0-2 vs. 3-6).

(3) Inferential Statistics

- **Primary Efficacy Endpoint:** The proportion of subjects with mRS score 0-2 at Day 90 is compared between dose groups using the chi-square test or Fisher's exact test. A generalized linear model is used to adjust for potential confounders (e.g., age, baseline NIHSS score).
- **Secondary Efficacy Endpoints:**
 - Mean changes in NIHSS, MBI, and EQ-5D-5L scores from baseline are compared using repeated measures analysis of variance (ANOVA) or Kruskal-Wallis rank sum test.
 - The proportion of subjects with NIHSS score reduction ≥ 4 points at Day 14 is compared using the chi-square test.
- **Safety Endpoints:**
 - The incidence of AEs and SAEs is compared between dose groups using the chi-square test or Fisher's exact test.

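### LOCF has no exception for death, so a subject who dies after Day 14 can enter the Day 90 NIHSS, MBI and EQ-5D-5L analyses with a living score

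*Protocol*

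**What the plan says.** Section 11(1) defines the Full Analysis Set (FAS) as subjects with at least one dose and adds: "Missing efficacy data are imputed using the last observation carried forward (LOCF) method". Nothing there separates a value missing because of death from one missing for another reason.

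Section 5(3) lists these endpoints: "Mean change in NIHSS score from baseline to Day 14 and Day 90"; "Mean change in MBI score from baseline to Day 90"; "Mean change in EQ-5D-5L utility value from baseline to Day 90". It also lists the proportion with MBI of at least 60 at Day 90 and the proportion with an NIHSS fall of at least 4 points at Day 14.

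Section 4(3) gives NIHSS a range of 0 to 42 and MBI a range of 0 to 100, and describes EQ-5D-5L as "scored as a utility value ranging from -0.291 to 1.0". None of the three is assigned a value for death. NIHSS is taken at baseline and Days 7, 14 and 90. MBI and EQ-5D-5L are taken at baseline and Days 14 and 90 only.

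Death appears as its own endpoint, 90-day all-cause mortality, in section 5(2). Section 2(5) removes from the efficacy set a subject with no evaluable efficacy data. Section 2(4) withdraws a subject whose stroke worsens after dosing and classes that subject as an invalid case.

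**The concern.** LOCF assumes that an unobserved score exists and is close to the last one seen. After death there is no such score. Applied as written, the rule gives a dead subject a neurological deficit, a level of independence and a quality-of-life value at Day 90, all measured while alive. These values then enter the dose-group comparisons in section 11(3).

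Preliminary effectiveness is part of the stated primary objective, and each dose group has 3 to 6 subjects, so a single case is not diluted. Enrolment is open and sequential. A rule for deaths chosen after one has occurred would be chosen with knowledge of that subject's dose and scores.

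**Working it through.** The plan states no figure on this point, so there is none to reproduce. The check traces the rule and then sizes it.

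**1. What is carried, by time of death** (sections 4(3), 11(1), 2(5); the FAS is read as all dosed subjects, although the text says randomized)

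| Death occurs | NIHSS used at Day 90 | MBI and EQ-5D-5L used at Day 90 |
|---|---|---|
| Before any post-baseline assessment | Baseline under 11(1), or subject removed under 2(5) | Same |
| After Day 7, before Day 14 | Day 7 value | Baseline value, change 0 |
| After Day 14, before Day 90 | Day 14 value | Day 14 value |

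The last interval is nominally 90 − 14 = 76 days with no scale assessment. A subject who dies in it normally has Day 7 and Day 14 scores, so the no-evaluable-data exclusion does not apply.

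**2. Responder endpoints.** A subject with MBI of 60 or more at Day 14 who then dies counts as a Day 90 success. The proportion shifts by 1/3 = 33 percentage points with 3 subjects and 1/6 = 17 with 6. Likewise, a subject with an NIHSS fall of at least 4 at Day 7 who dies before Day 14 counts as a Day 14 responder.

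**3. Mean changes, cohort of 3, one death after Day 14.** All scores here are assumptions; the protocol gives none.

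- NIHSS: baseline 12 for the subject who dies, survivors change by −4.
  - LOCF, Day 14 change −4: (−4 −4 −4)/3 = −4.0.
  - LOCF, Day 14 change 0: (−4 −4 + 0)/3 = −2.7.
  - Survivors only: −4.0.
  - Death set to 42: change 42 − 12 = +30, mean (−4 −4 + 30)/3 = +7.3.
  - The median is −4 in all four cases.
- MBI: baseline 40 and Day 14 value 55 for the subject who dies, survivors +30.
  - LOCF: (30 + 30 + 15)/3 = +25.
  - Survivors only: +30.
  - Death set to 0: (30 + 30 − 40)/3 = +6.7.
- EQ-5D-5L: baseline 0.3 and Day 14 value 0.5 for the subject who dies, survivors +0.3.
  - LOCF: (0.3 + 0.3 + 0.2)/3 = +0.267.
  - Death set to 0: (0.3 + 0.3 − 0.3)/3 = +0.100.
  - Death set to −0.291: (0.3 + 0.3 − 0.591)/3 = +0.003.

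In a cohort of 6 with the same NIHSS assumptions and a Day 14 change of −4, LOCF gives (5 × −4 − 4)/6 = −4.0, and death at 42 gives (−20 + 30)/6 = +1.7.

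In the first NIHSS case the death leaves no trace in the mean. The distance from LOCF to a scored death is set mainly by the score chosen, as the two EQ-5D-5L values show.

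**4. Ranks.** With no DLT there are 3 × 3 = 9 subjects. Under LOCF the dead subject can take any rank from 1 to 9, according to the last living score. Under a worst-rank rule the subject is always last.

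**5. How often this could arise.** The protocol gives no death rate. With an assumed probability q of death between Day 14 and Day 90, the chance of at least one is 1 − (1 − q)^n:

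| q | n = 3 | n = 9 | n = 18 |
|---|---|---|---|
| 2% | 6% | 17% | 30% |
| 5% | 14% | 37% | 60% |
| 10% | 27% | 61% | 85% |

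**The case against.** The best defence is that nothing is hidden. Mortality to Day 90 is a separate endpoint, and mRS, on a 0 to 6 scale, carries the efficacy endpoint that section 11(3) calls primary. Escalation rests on DLT within 14 days. The Per Protocol Set requires all visits, so it already leaves out subjects who die before Day 90. Medians and the Kruskal-Wallis test are already in section 11. The handling of death on secondary scales is often left to a SAP, and section 11(1) does not say that death counts as missing data.

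Most of this stands as mitigation. It does not correct the FAS result on the three scales. The protocol has itself fixed an imputation rule for all missing efficacy data, and its plain application carries scores past death. The Per Protocol Set is only a sensitivity set and drops subjects for other reasons too.

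A reader might go further and infer that one death reverses the sign of a dose group's mean. That follows only if death is set to a number such as NIHSS 42, which the protocol does not do. In the NIHSS examples the median does not move, and LOCF is no more favourable than the survivors-only mean.

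**Conclusion.** The point holds for a subject who has Day 14 data, dies before Day 90 and is not removed under section 2(4) or 2(5). For MBI and EQ-5D-5L it also holds for a death between Day 7 and Day 14, which is recorded as no change. The firm size is one responder in 3 to 6. The effect on means rests on assumed scores. It should be corrected, but it concerns efficacy endpoints other than mRS in a small exploratory trial.

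Three wider readings are not supported:

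- That every death is carried forward. Section 2(5) may remove a subject who dies before any post-baseline assessment, and section 2(4) may remove one whose stroke worsened. Removal would instead drop the death from the efficacy result.
- That those who die will usually have improved first. The protocol has no Day 14 recovery data.
- That deaths are to be expected. No mortality figure is given, and eligibility stops at age 70 and requires prior mRS 0–1 and ASPECTS of at least 6.

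**What to change.** In section 11(1), state that LOCF is not applied past death. In section 11(3), for each of NIHSS, MBI and EQ-5D-5L:

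- Compare dose groups with the Kruskal-Wallis test already named, ranking deaths (tied) below every survivor.
- Count deaths as non-responders for MBI of at least 60 at Day 90 and, where death precedes Day 14, for the NIHSS reduction of at least 4.
- Report survivor-only summaries beside the number of deaths in each dose group.
- Put no numeric death score into a mean. NIHSS 42 is a convention that the protocol does not adopt, and an EQ-5D-5L value of 0 is not the bottom of a scale that reaches −0.291.

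Also state whether subjects classed as invalid for stroke deterioration under section 2(4) stay in the FAS, and reconcile the FAS with the exclusions in section 2(5), so that deaths are not dropped from efficacy.

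The cost is a few sentences and a few lines of code before data exist. Efficacy summaries may become slightly less favourable, and where a death occurs there is no single mean over all treated subjects.

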1. **Dose Adjustment:** No dose reduction is allowed during the study. If a subject experiences a Grade ≥ 3 AE, study drug administration is suspended until the AE resolves to Grade ≤ 1 ; if the AE is judged to be related to the study drug, the subject withdraws from the study.

2. **Prohibited and Restricted Medications:**

- Prohibited medications: Antineoplastic drugs, immunosuppressants (e.g., cyclosporine, tacrolimus), neurotrophic factors (e.g., nerve growth factor);
- Restricted medications: Antibiotics and antiviral drugs (used only for confirmed infections, with duration documented); non-steroidal anti-inflammatory drugs (NSAIDs) (avoided if possible to reduce bleeding risk).

3. **Concurrent Diseases Management:** If a subject develops a concurrent disease (e.g., pneumonia, myocardial ischemia) during the study, the treating physician provides standard treatment, and the details are documented in the "Concurrent Disease Record Form" in the CRF.
4. **Subject Education:** Subjects are instructed to report any new symptoms (e.g., headache, nasal congestion, rash) to the investigator immediately, and to avoid self-medication with prohibited drugs.

4. Observation Items

(1) Demographic and Clinical Data

1. **Demographic Characteristics:** Gender, age, date of birth, ethnicity, dominant hand, occupation, height, weight, body mass index (BMI);
2. **Clinical History:** Chief complaint, onset time of stroke, detailed history of present illness, primary diagnosis (including infarct location), secondary diagnoses, past medical history (hypertension, diabetes, hyperlipidemia, coronary heart disease), surgical history, allergy history, family history, smoking history (pack-years), drinking history (alcohol consumption per week);
3. **Medication History:** Current medications (including over-the-counter drugs, herbal supplements) at screening, with dosage, frequency, and duration documented.

All data are recorded in the "Baseline Demographic and Clinical Data Form" in the CRF.

(2) Safety Observation Indicators

1. **Vital Signs:** Measured before each dose administration and at each follow-up visit:
 - Pulse (beats per minute), blood pressure (mmHg, measured in the sitting position after 5 minutes of rest), respiratory rate (breaths per minute), body temperature (°C, axillary or oral);
 - Abnormal vital signs (e.g., hypertension: systolic blood pressure ≥ 160 mmHg) are documented and followed up.
2. **Laboratory Tests:**

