 - **Hematology:** Complete blood count (CBC) with differential (red blood cell [RBC], hemoglobin [Hb], white blood cell [WBC], neutrophil percentage [NEUT%], lymphocyte percentage [LYMPH%], platelet count [PLT]);
 - **Clinical Chemistry:** Liver function (ALT, AST, total bilirubin [TBIL], alkaline phosphatase [ALP], γ -glutamyl transferase [γ -GT]), renal function

(Scr, BUN), fasting blood glucose (FBG), glycated hemoglobin (HbA1c), lipid profile (total cholesterol [TC], triglycerides [TG], HDL, LDL, lipoprotein (a) [LP(a)]);

- **Coagulation Function:** PT, INR, APTT, thrombin time (TT), fibrinogen (FIB);
- **Serum Electrolytes:** Potassium (K⁺), sodium (Na⁺), calcium (Ca²⁺), magnesium (Mg²⁺), phosphorus (P³⁺), chlorine (Cl⁻);
- **Infectious Disease Screening:** HBsAg, hepatitis B surface antibody (HBsAb), hepatitis B e antigen (HBeAg), hepatitis B e antibody (HBeAb), hepatitis B core antibody (HBcAb), HCV antibody, HIV antibody, TPPA, RPR;
- **Tumor Markers:** Alpha-fetoprotein (AFP), carbohydrate antigen 199 (CA199), carcinoembryonic antigen (CEA);
- **Urinalysis:** Urine protein (PRO), urine glucose (GLU), quantitative urine RBC, quantitative urine WBC, urine ketones (KET);
- **Pregnancy Test:** Urine pregnancy test for women of childbearing potential at screening and Day 90.

3. Imaging Examinations:

- **Chest X-ray:** Performed at screening and Day 90 (to exclude active pulmonary infection or malignancy);
- **Electrocardiogram (ECG):** 12-lead ECG performed at screening, Day 14, and Day 90 (to evaluate cardiac function and detect arrhythmias);
- **Cerebral Imaging:**
 - Baseline: NCCT, DWI, MRA/CTA (to confirm infarct location and vascular occlusion);
 - Day 14 and Day 90: DWI, fluid-attenuated inversion recovery (FLAIR), CTA/CT perfusion (CTP) (to assess infarct volume, edema, and cerebral perfusion).

4. Adverse Events Monitoring:

- AEs are monitored from the time of informed consent signing until 30 days after the last dose of the study drug.
- All AEs (including nasal irritation, headache, rash) are documented in the "Adverse

Event Record Form" in the CRF, with details including onset time, severity (CTCAE V5.0), duration, relationship to the study drug (definite, probable, possible, unlikely, unrelated), treatment measures, and outcome.

- SAEs are reported to the Ethics Committee, sponsor, and NMPA in accordance with regulatory requirements (within 24 hours of awareness).

(3) Efficacy Observation Indicators

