2. Efficacy Assessments:

- Neurological scales: NIHSS, mRS, MBI, EQ-5D-5L;
- Infarct volume measurement (DWI) and CTP parameter analysis.

3. Documentation: Record combined medications, rehabilitation therapy, and schedule the Day 90 visit.

Fourth Visit (Day 90 ± 7)

1. Safety Assessments:

- Vital signs measurement;
- Laboratory tests: CBC, clinical chemistry, coagulation function, serum electrolytes, infectious disease screening, tumor markers, urinalysis, pregnancy test (if applicable);
- Imaging examinations: Chest X-ray, 12-lead ECG, DWI, FLAIR, CTA/CTP;
- Final AE follow-up (until 30 days after the last dose).

2. Efficacy Assessments:

- Neurological scales: NIHSS, mRS, MBI, EQ-5D-5L;
- Final infarct volume measurement and CTP parameter analysis.

3. Study Completion: Confirm completion of all assessments, and document any protocol deviations.

Items/Visits	Baseline (Day 0)	Day 7 (±1)	Day 14 (±2)	Day 90 (±7)
Sign Informed Consent Form	●			
Review Inclusion/Exclusion Criteria	●			
Collect Demographic & Clinical Data	●	●	●	●
Vital Signs	●	●	●	●
Urine Pregnancy Test	●			●
Hematology (CBC) *	●	●	●	●
Clinical Chemistry (Liver/Kidney Function, Glucose, Lipids) *	●	●	●	●
Coagulation Function (PT, INR, APTT, FIB)	●		●	●
Serum Electrolytes	●		●	●
Infectious Disease Screening (8 Items)	●		●	●
Tumor Markers (AFP, CA199, CEA) *	●		●	●
Urinalysis *	●	●	●	●

Items/Visits	Baseline (Day 0)	Day 7 (±1)	Day 14 (±2)	Day 90 (±7)
Chest X-ray	•		•	
12-Lead ECG	•		•	•
Cerebral Imaging (CT/MRI/CTA/CTP)	•	•	•	•
Neurological Scales (NIHSS, mRS)	•	•	•	•
Modified Barthel Index (MBI)	•		•	•
EQ-5D-5L Score	•		•	•
Record Adverse Events	•	•	•	•
Record Concomitant Medications	•	•	•	•
Record Rehabilitation Therapy	•	•	•	•

7. Regulations for Packaging, Acceptance, Storage, Distribution, and Recovery of Study MSC-sEV Preparations

(1) Packaging of Study MSC-sEV Preparations

- **Primary Packaging:** Sterile glass vials (2.0 mL) with rubber stoppers and aluminum caps, labeled with the study drug name, batch number, dose level, expiration date, storage conditions, and "For Clinical Trial Use Only".
- **Secondary Packaging:** Individual cartons containing one vial of study drug and one vial of hyaluronidase, with a leaflet describing the administration method.
- **Tertiary Packaging:** Insulated containers with dry ice for transportation, labeled with "Biological

Product", "Keep Frozen (-80°C)", and the sponsor's contact information.

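### LOCF for all missing efficacy data scores a living subject's missing Day 90 outcome at Day 14 or earlier and, on the text schedule, turns a missed Day 14 scan into zero change; the bias can run either way

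*Protocol*

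**What the plan says.** - **Missing-data rule.** Section 11(1) of the protocol, under the full analysis set: "Missing efficacy data are imputed using the last observation carried forward (LOCF) method". It makes no exception by endpoint, visit or reason.
- **Scales.** Section 4(3) schedules NIHSS and mRS at baseline, Day 7, Day 14 and Day 90. MBI and EQ-5D-5L have no Day 7 assessment: "Administered at baseline, Day 14, and Day 90".
- **Infarct volume.** Section 4(3): "Infarct volume is measured on DWI using the ABC/2 method", and "Changes in infarct volume from baseline to Day 14 are used to evaluate infarct progression or regression". Perfusion is listed there for baseline, Day 14 and Day 90.
- **Imaging times in the text.** Section 4(2): "Baseline: NCCT, DWI, MRA/CTA (to confirm infarct location and vascular occlusion)" and "Day 14 and Day 90: DWI, fluid-attenuated inversion recovery (FLAIR), CTA/CT perfusion (CTP)". The Day 7 visit description in section 6 lists no imaging.
- **Imaging times in the table.** The visit table in section 6 has a row "Cerebral Imaging (CT/MRI/CTA/CTP)" that is marked at all four visits, Day 7 included.
- **Leaving the study.** Section 3(4), on Grade 3 or higher adverse events: "if the AE is judged to be related to the study drug, the subject withdraws from the study". Section 2(4) also withdraws subjects whose stroke worsens after treatment, and foresees missed visits, refused assessments and lost contact.
- **Sensitivity analysis.** Section 11(1) names only the per-protocol set, which requires all visits and all four doses.

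**The concern.** LOCF is unbiased only if a subject's status would have stayed where it was last seen. This design expects the opposite. Subjects enter 24 hours to 14 days after stroke with NIHSS of 6 or more, all receive rehabilitation from Day 1, and the efficacy endpoints are built to measure change. An early score standing in for a Day 90 score is therefore likely to be wrong, and the analysis then treats it as observed.

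Section 11(3) calls mRS 0-2 at Day 90 the primary efficacy endpoint, and the summary places preliminary effectiveness within the primary objective. With 3 to 6 subjects per dose, one imputed value carries great weight in any dose comparison. The point concerns living subjects only; how deaths are scored is a separate matter.

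**Working it through.** The protocol gives no figure to reproduce here. The check traces the rule through the schedule and then sizes the effect under stated assumptions.

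**1. Age of a carried Day 14 value at Day 90.** Nominal gap: 90 - 14 = 76 days. With the visit windows: (90 - 7) - (14 + 2) = 67 to (90 + 7) - (14 - 2) = 85 days. Day 14 falls 1 + 14 = 15 to 14 + 14 = 28 days after stroke onset.

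**2. Which value is carried.**

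| Missing value | Last earlier value |
|---|---|
| Day 90 mRS, NIHSS | Day 14, else Day 7 |
| Day 90 MBI, EQ-5D-5L | Day 14, else baseline |
| Day 14 infarct volume, perfusion (text schedule) | Baseline, so change = 0 |
| Day 14 infarct volume (table schedule, if Day 7 includes DWI) | Day 7 |

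Section 2(5) excludes from the efficacy analysis set a subject with no NIHSS or mRS after baseline. It does not remove a subject who has Day 7 scales but no later visit. That subject's MBI, EQ-5D-5L and, on the text schedule, infarct change are all set to zero.

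**3. Mean infarct change.** If m of n subjects carry baseline, the reported mean is (n - m)/n times the mean of the observed changes. One missed scan gives 2/3 = 0.667 in a group of 3 and 5/6 = 0.833 in a group of 6. For example, an assumed observed mean of -10 mL becomes -6.67 mL in a group of 3. This factor equals the bias only if the missing subject would have changed as the others did.

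**4. Proportion with mRS 0-2 at Day 90.** Let p14 and p90 be the assumed proportions at Day 14 and Day 90. With one subject missing, unrelated to outcome, and the Day 14 value carried, the expected proportion is ((n - 1) x p90 + p14)/n.

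| p14 / p90 (assumed) | n = 3 | n = 6 |
|---|---|---|
| 0.20 / 0.45 | (2 x 0.45 + 0.20)/3 = 0.367, -8.3 points | (5 x 0.45 + 0.20)/6 = 0.408, -4.2 points |
| 0.10 / 0.30 | 0.233, -6.7 points | 0.267, -3.3 points |
| 0.30 / 0.50 | 0.433, -6.7 points | 0.467, -3.3 points |
| 0.10 / 0.40 | 0.300, -10.0 points | 0.350, -5.0 points |

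**5. Largest effect of one wrong value.** 1/3 = 33.3 points or 1/6 = 16.7 points, in either direction. A subject at mRS 2 on Day 7 who then deteriorates and leaves counts as a success under LOCF. If the true Day 90 state is 3 or more, the proportion is overstated by that amount.

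**6. How often this arises.** With an assumed missing rate d, the chance of at least one missing value is 1 - (1 - d)^n. For d = 5%, 10% and 20% this is 14%, 27% and 49% in a group of 3, and 60%, 85% and 98% in 18 subjects.

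**The case against.** - **The table may supply a Day 7 scan.** A reader might infer that a missed Day 14 scan always gives exactly zero. That holds only on the text schedule. If the Day 7 mark in the table includes DWI, a Day 7 infarct volume is carried. This stands as a limit, though a Day 7 value is still not a Day 14 value.
- **Baseline mRS is mostly kept out.** A reader might infer that entry status can be carried to Day 90 mRS, with a larger bias. Section 2(5) excludes subjects with no post-baseline NIHSS or mRS. Section 11 does not say how that efficacy analysis set relates to the full analysis set, but the stated intent largely closes this route, and no size is claimed for it.
- **The direction is not fixed.** A reader might infer that LOCF always understates recovery. Section 2(4) withdraws subjects whose stroke deteriorates, and LOCF may keep their better, earlier score. That section calls them invalid cases without saying whether they leave the full analysis set. This objection stands.
- **A false dose-response is only a possibility.** Withdrawal follows drug-related Grade 3 or higher events, so carried values could cluster at higher doses. But a drug-related Grade 3-4 event within 14 days is itself a dose-limiting toxicity, and one in three expands the group to six. A dose that clears has at most one such subject in six, where the shift is about -4 points, not -8.
- **The 33 points come from n = 3.** Correct: with observed values only, two subjects remain and each is worth 50 points. LOCF hides that fragility; it does not create it.
- **The per-protocol set already gives a completer analysis.** It does, but by removing subjects who missed visits or doses. It therefore neither tests LOCF nor bounds the missing outcomes.
- **Observed values are also biased if withdrawal is informative.** True, which is why bounds are needed alongside them.

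**Conclusion.** The concern holds for the efficacy and exploratory results. LOCF is fixed for every missing efficacy value. On the protocol's own schedule it replaces a living subject's Day 90 outcome with one at least 67 to 85 days old, and on the text schedule it sets a missed Day 14 infarct or perfusion change to zero. Under the assumed rates, with missingness unrelated to outcome, one missing subject shifts the expected mRS 0-2 proportion by -7 to -10 points in a group of 3 and -3 to -5 in a group of 6. In a single realised group the error can reach 33 or 17 points either way. All recovery and dropout rates here are assumptions.

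A reader might go further and doubt the safety conclusions. The documents do not support that: dose-limiting toxicity is the primary outcome, and the escalation rule uses no imputed efficacy data. With groups this small, the gain is more honest efficacy reporting, not a different escalation decision.

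**What to change.** In section 11(1):

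1. Replace LOCF for living subjects with analysis of observed values, and report the number missing and the reason by dose group.
2. For mRS 0-2 and the NIHSS and MBI responder endpoints, add two bounds that count every missing living subject first as a success and then as a failure. With one missing, the range is 33.3 points wide in a group of 3 and 16.7 in a group of 6.
3. Do not carry a baseline value into any change-from-baseline endpoint; leave a missed Day 14 infarct volume or perfusion value missing.
4. If LOCF is kept, label it a sensitivity analysis.

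Also reconcile the Day 7 imaging mark in the section 6 table with sections 4(2) and 6, and state how the efficacy analysis set in section 2(5) relates to the full analysis set.

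The cost is one paragraph and one extra line per responder table. The reported range becomes wider and less favourable.
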